## Laboratory Safety Evaluations

Hematology laboratory measurements include WBC (white blood cells), Hgb (hemoglobin), platelet count, and absolute neutrophil count (ANC). Chemistry laboratory measurements include sodium, potassium, creatinine, Total bilirubin, and alanine aminotransferase (ALT). Chemistry and hematology assessments occurred at screening and 7 days post each vaccination (Study Visits 00, 03, 07, and 11); these assessments were also performed at unscheduled and early termination visits as indicated. The severity of laboratory AEs are graded using the protocol-defined scale in [Table 7](#).

The last measurement prior to receiving the first vaccination for each parameter will be considered baseline.

### 4.5.2 Immunogenicity Variables

Serum from blood collected at Days 1, 8, 29, 36, 57, 64, 85, and 113 will be analyzed using an enzyme-linked immunosorbent assay (ELISA) to measure *C. jejuni* capsule-specific IgG serum antibody titers, CRM197-specific IgG serum antibody titers, *C. jejuni* capsule-specific IgM serum antibody titers, and CRM197-specific IgM serum antibody titers.

PBMCs (Peripheral Blood Mononuclear Cells) collected at Days 1, 8, 36, and 64 will be analyzed using ELISA to measure *C. jejuni* capsule-specific IgG ALS (Antibodies in Lymphocyte Supernatant).

Immunogenicity specimens (serum or PBMCs) collected at supplemental visits because the specimen was not collected at the main study visit will still be considered for inclusion in analyses based on study visit window.

All immunogenicity variables will be reported by the laboratory in log10 titers and will be converted to titers prior to any analysis. The conversion will be done when generating analysis datasets, and the converted result in titers will be rounded to the nearest whole number for analysis and reporting.

## 5. SAMPLE SIZE CONSIDERATIONS

Sixty (60) participants will be enrolled (20 per cohort). The sample size for each cohort was chosen based on the number of participants deemed appropriate for a first-in-human Phase 1 study. Given the small number of participants per group, the precision of our estimate for adverse events is limited. For example, using an exact binomial interval for no observed adverse events within the 10 participants per group yields a 95% confidence interval (CI) of 0-31% (Clopper-Pearson) ([Table 3](#)). Follow-on studies evaluating seemingly safe and immunogenic doses will be required with larger numbers of volunteers in order to better define the safety profile.

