9.3 Treatment Assignment Procedures

9.3.1 Randomization Procedures

Per International Council for Harmonisation (ICH) guideline E6: GCP, screening records will be kept at the VTEU site to document the reason why an individual was screened, but failed trial entry criteria. The reasons why individuals failed screening will be recorded in the SDCC Advantage eClinical® (Electronic Data Capture System). Once consented and upon entry of demographic data and confirmation of eligibility for this trial, the subject will be enrolled. Subjects will be assigned randomly using permuted blocks to receive three IM doses of either CJCV2 (1 µg in Cohort 1, 3 µg in Cohort 2, or 10 µg in Cohort 3) vaccine alone or CJCV2 vaccine + ALFQ (200 µg 3D-PHAD® and 100 µg QS-21 in all Cohorts) adjuvant. The randomization scheme for this study is listed below and presented in **Table 1**. Subjects will be randomized such that the first six subjects of each cohort will be allocated to each of the two treatment arms as the sentinel group.

- CJCV2 alone group (N=30, 10 per cohort) will receive three-doses of CJCV2 vaccine + diluent administered by IM on Days 1, 29, and 57.
- CJCV2 + ALFQ group (N=30, 10 per cohort) will receive three-doses of CJCV2 vaccine + ALFQ adjuvant administered by IM on Days 1, 29, and 57.

Enrollment of subjects will be done online using the enrollment module of Advantage eClinical®.

The randomization code will be prepared by statisticians at the SDCC and included in the enrollment module for this trial. Advantage eClinical® will assign each subject to a group after the demographic and eligibility data have been entered into the system. A designated individual at the site will be provided with a code list for emergency unblinding purposes, which will be kept in a secure place. Instructions for use of the enrollment module are included in the Advantage eClinical® User's Guide. Manual back-up procedures and instructions are provided for use if the site temporarily loses access to the Internet, or the online enrollment system is unavailable.

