9.4.2 Safety Data

Safety data will be summarized for the Safety Analysis Population. Subjects receiving a vaccination according to a study arm other than the study arm to which they were randomized, will be analyzed according to the vaccination(s) they actually received. Safety summaries will be presented for each dose group by presence or absence of ALFQ.

The proportion of subjects reporting at least one solicited AE will be summarized for each solicited AE, any systemic symptom, any local symptom, and any symptom. The 95% CI will be presented, and a Fisher's exact test will be performed to test for differences in the proportion of subjects reporting a solicited AE within dose groups between those with and without adjuvant.

Solicited AEs will be summarized by maximum severity for each day after each study vaccination for Days 1-8. The number, percentage (observed rate), and exact two-sided 95% CI for subjects reporting each solicited AE within 8 days following vaccination will be summarized. In addition, maximum severity for each solicited AE will be determined for each subject and reported by study arm and the resulting number and percentage of subjects will be summarized by severity grade (none, mild, moderate, severe). Summaries of solicited AEs will be presented separately by study arm for each study vaccination as well as overall study vaccinations.

Vaccine-related unsolicited AEs will be coded by MedDRA® for preferred term and system organ class (SOC). The number of SAEs, MAAEs, NOCMCs, and PIMMCs are likely to be small in this trial and will be reported by detailed listings showing the event description, MedDRA® preferred term and SOC, relevant dates (study vaccinations and AE duration), severity, relatedness, and outcome. If the number of events permits, a Fisher's exact test may be used to test for differences in unsolicited AE rates between adjuvant and non-adjuvant groups within dose levels, in a similar manner as for solicited AEs.

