### 4.4.3. Method of Assigning Participants to Treatment Groups (Randomization)

Enrollment/randomization was performed through the enrollment module in the electronic data capture system maintained by the SDCC (Statistical and Data Coordinating Center).

Eligible participants were randomized and assigned in a 1:1 ratio to CJCV2:CJCV2+ALFQ. The randomization used a block randomization scheme with random block sizes and was stratified by cohort.

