### 4.4.5. Selection and Timing of Dose for Each Participant

All participants will receive three doses of vaccine on Days 1, 29, and 57. A fixed dose of CJCV2 will be used for each cohort: 1  $\mu$ g in Cohort 1, 3  $\mu$ g in Cohort 2, and 10  $\mu$ g in Cohort 3. Any participant assigned to receive ALFQ will receive the same fixed dose (200  $\mu$ g 3D-PHAD and 100  $\mu$ g QS-21). Participants in each cohort will be randomized using a 1:1 allocation ratio to receive either CJCV2 alone or CJCV2+ALFQ.

Sentinels will be dosed at least two hours apart with no more than two sentinels per day vaccinated.

Between the time of vaccination of the first six sentinels to 7 days after enrollment of the last sentinels, no new participants will be vaccinated, but screening may continue.

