## 6. GENERAL STATISTICAL CONSIDERATIONS

### 6.1. General Principles

Continuous variables will be summarized using appropriate descriptive statistics such as n (non-missing sample size), mean/geometric mean, standard deviation, median, maximum, and minimum. The number (n) and percentages (%; based on the non-missing sample size) of observed levels will be reported for all categorical measures. In general, all data will be listed, sorted by treatment group and participant, and when appropriate by visit number within participant. All summary tables will be structured with a column for each treatment in the order (1 $\mu$ g CJC2, 1 $\mu$ g CJC2+ALFQ, 3 $\mu$ g CJC2, 3 $\mu$ g CJC2+ALFQ, 10 $\mu$ g CJC2, 10 $\mu$ g CJC2+ALFQ) and will be annotated with the total population size relevant to that table/treatment group, including any missing observations.

Confidence intervals for Geometric Mean Titer (GMT) and Geometric Mean Fold-Rise (GMFR) will be calculated using a student's t distribution. Confidence intervals for proportions of participants will be exact CIs using the Clopper-Pearson method.

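### No planned safety table or interval pools participants by ALFQ status, so the narrowest zero-event interval planned for ALFQ recipients is 0–31%, where the 30 planned recipients together would give 0–12%

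*SAP*

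**What the plan says.** The protocol sets the level of safety reporting in section 9.4.2: "Safety summaries will be presented for each dose group by presence or absence of ALFQ". SAP 6.1 carries this through: "All summary tables will be structured with a column for each treatment in the order", followed by the six dose-by-adjuvant groups. The adverse event tables that carry confidence intervals (Tables 32–34 for solicited events, 47–49 for unsolicited events) are produced cohort by cohort, with two columns of about 10 people each. SAP 5 states precision at that level: "using an exact binomial interval for no observed adverse events within the 10 participants per group yields a 95% confidence interval (CI) of 0-31" percent. Table 3 has a single row, for N = 10.

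On the adjuvant, SAP 4.4.5 states: "Any participant assigned to receive ALFQ will receive the same fixed dose". SAP 4.4.3 states: "Eligible participants were randomized and assigned in a 1:1 ratio to CJCV2:CJCV2+ALFQ", with stratification by cohort. Protocol 9.3.1 describes the adjuvanted participants as one group: "CJCV2 + ALFQ group (N=30, 10 per cohort) will receive three-doses of CJCV2 vaccine + ALFQ adjuvant administered by IM on Days 1, 29, and 57". It describes a CJCV2-alone group of the same size in the same way.

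Table 30 (overall adverse event summary) and Table 31 (SAEs and common non-serious events) add an 'All Participants' column to the six groups. Table 30 gives n and % only. Table 31 gives n, % and event counts.

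**The concern.** Safety is the primary objective, and SAP 2.1 says the analyses will assess whether ALFQ can improve the immune response without materially changing safety. The 30 people who receive the same adjuvant dose are a natural denominator for that question, and the 30 on CJCV2 alone, randomized within the same cohorts, are their concurrent counterpart. The plan defines neither denominator for any safety display. The one pooled column it has combines the two, so it cannot show how ALFQ recipients fared.

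The gap matters most for the infrequent primary endpoints. SAEs, MAAEs, NOCMCs and PIMMCs appear as categories only in Table 30, without intervals, and in listings (Tables 62 and 64). For these categories no interval is planned even at n = 10. A report with no such events among ALFQ recipients would have the per-group 0–31% of SAP 5 as its only prespecified statement of uncertainty.

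**Working it through.** **Inputs**

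- Interval type: two-sided 95% exact. Protocol 9.4.2: "The number, percentage (observed rate), and exact two-sided 95% CI for subjects reporting each solicited AE". SAP 6.1: "Confidence intervals for proportions of participants will be exact CIs using the Clopper-Pearson method".
- n = 10 per treatment group (SAP 5, Table 3).
- n = 30 planned ALFQ recipients, 10 in each of three cohorts (Protocol 9.3.1).
- n = 60 planned in total (SAP 5).

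**Formula for zero events.** The lower limit is 0. The upper limit U solves (1 − U)^n = 0.025, so U = 1 − 0.025^(1/n).

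**The plan's own figure**

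- n = 10: U = 1 − 0.025^(1/10) = 0.3085, or 30.85%. This rounds to the stated 31%, so the SAP figure is reproduced. A one-sided 95% limit would be 25.9% and the rule of three would give 30%, so the stated figure is the two-sided exact one.

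**The same calculation at the other denominators**

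- n = 30 (all ALFQ recipients): U = 1 − 0.025^(1/30) = 0.1157, or 11.57%, that is 0–12%.
- n = 60 ('All Participants'): U = 1 − 0.025^(1/60) = 0.0596, or 5.96%. No interval is planned for this column, and it mixes adjuvanted and unadjuvanted participants.

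Pooling by ALFQ status shortens the zero-event interval by a factor of 30.85 / 11.57 = 2.67.

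**One event.** The limits are the 2.5% quantile of Beta(1, n) and the 97.5% quantile of Beta(2, n − 1).

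- 1/10: 0.3% to 44.5%.
- 1/30: 0.1% to 17.2%.

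**Sensitivity to the planned denominator**

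- One ALFQ recipient not vaccinated, n = 29: U = 1 − 0.025^(1/29) = 11.94%, still 0–12%.
- ALFQ not given in one cohort, n = 20: U = 1 − 0.025^(1/20) = 16.84%, or 0–17%. Protocol 7.6.2 allows later cohorts to continue with CJCV2 alone after a halt, so this case is possible under the plan.

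**Check of the displays.** Tables 32–34 and 47–49 have intervals, but only by cohort. Tables 30 and 31 have the six groups plus 'All Participants', without intervals. The laboratory and vital-sign tables are by treatment group. None pools by ALFQ status. The displays that do are the immunogenicity correlations of SAP 11.4 (Tables 28 and 29, Figures 22–31).

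**The case against.** The strongest reply is that reporting by dose is deliberate. The primary objective concerns three doses with and without ALFQ, Protocol 9.4.2 requires summaries at that level, and SAP 5 says larger follow-on studies will be needed to define the safety profile. For any single dose with ALFQ the zero-event bound stays at 31% whatever columns are added. The pooled rate averages over a tenfold range of CJCV2 dose (1 to 10 µg). It also averages over cohorts enrolled one after another under different eligibility criteria (SAP 4.3), with some preparations outside the acceptable range of the target dose (SAP 11.4). Protocol 9.4.2 expected few SAEs, MAAEs, NOCMCs and PIMMCs and assigned them to listings, which the SAP provides. The correlation tables are a weak precedent, because they span cohorts in order to use the variation in dose, whereas a pooled safety column averages over it.

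All of this stands. It is a reason to keep the six columns and footnote the pooled ones. It is not a reason to leave the adjuvant question in SAP 2.1 without a display.

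Several stronger readings are tempting, and the documents do not support them:

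- *Every safety display stops at 10 people.* It does not. Tables 30 and 31 have an 'All Participants' column.
- *The plan cannot bound the risk below 31%.* A reader can add three counts in Table 30 and compute x/30. What is missing is a prespecified display, chosen before unblinding. No data are missing.
- *The plan makes an infrequent event less likely to be seen.* At a true 5% risk the chance of at least one event is 40% among 10 people and 79% among 30, but all 30 are observed and listed either way. Only the interval changes.
- *The sample size rests on this interval.* SAP 5 bases the size on what was deemed appropriate for a first-in-human study. The interval is an example of limited precision.

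**Conclusion.** The point holds as a missing descriptive display. Nothing the plan calculates is wrong: the 31% figure is correct for its per-group purpose. The narrowest interval planned for ALFQ recipients with zero events is 0–31%, and the same data pooled by ALFQ status would give 0–12%.

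The 12% assumes that all 30 planned ALFQ recipients are vaccinated and evaluable. A reader might take it as the risk due to the adjuvant, but it is not that. It bounds the average risk among people given CJCV2+ALFQ across the three antigen doses. A risk attributable to ALFQ would need a comparison with CJCV2 alone, which is why the second pooled column belongs beside the first. Balanced allocation within each cohort keeps the two columns comparable in dose mix as long as both arms are enrolled in every cohort.

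This is a cheap improvement to a descriptive Phase 1 report. It does not affect the validity of the analyses already planned.

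**What to change.** - **Table 30.** Keep the six dose columns and add 'All CJCV2' and 'All CJCV2+ALFQ' (planned N = 30 each). In these two columns give exact Clopper-Pearson 95% intervals for SAE, related SAE, MAAE, NOCMC, PIMMC and related Grade 3 unsolicited events. Add one new row, any Grade 3 solicited event, because the table has no severity rows for solicited events. Define whether size-graded local reactions count in it, since SAP 4.5.1 presents large measurements as severe.
- **Table 3.** Add a line for N = 30 by ALFQ status, 0–12%, and adjust the column label, which now refers to treatment groups.
- **SAP 6.1.** Add a sentence allowing the two pooled columns as an exception to the six-column rule.
- **Footnote to Table 30.** State that the pooled rate averages over three CJCV2 doses and over sequential cohorts with differing eligibility, and that it describes CJCV2+ALFQ recipients and not adjuvant-attributable risk. Give the actual N from each cohort if ALFQ is dropped in a later one.
- **Table 31.** No change. It is built to fill a clinicaltrials.gov template.

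The cost is two columns, interval cells on seven rows, one row definition, one line in Table 3 and a footnote. It needs no new data and no hypothesis test, so it is consistent with SAP 6.8 and with the removal of the Fisher tests in SAP 15. The downside is that a pooled rate can hide a dose trend, so the dose columns must stay beside it.

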## 6. GENERAL STATISTICAL CONSIDERATIONS

### 6.1. General Principles

Continuous variables will be summarized using appropriate descriptive statistics such as n (non-missing sample size), mean/geometric mean, standard deviation, median, maximum, and minimum. The number (n) and percentages (%; based on the non-missing sample size) of observed levels will be reported for all categorical measures. In general, all data will be listed, sorted by treatment group and participant, and when appropriate by visit number within participant. All summary tables will be structured with a column for each treatment in the order (1 $\mu$ g CJC2, 1 $\mu$ g CJC2+ALFQ, 3 $\mu$ g CJC2, 3 $\mu$ g CJC2+ALFQ, 10 $\mu$ g CJC2, 10 $\mu$ g CJC2+ALFQ) and will be annotated with the total population size relevant to that table/treatment group, including any missing observations.

Confidence intervals for Geometric Mean Titer (GMT) and Geometric Mean Fold-Rise (GMFR) will be calculated using a student's t distribution. Confidence intervals for proportions of participants will be exact CIs using the Clopper-Pearson method.

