3 STUDY INTERVENTION/INVESTIGATIONAL PRODUCT

3.1 Study Product Description

3.1.1 CJCV2

The vaccine to be evaluated in the current project is a *C. jejuni* CCV named CJCV2 produced from an engineered mutant of 81-176 that is lacking an enzyme responsible for the production of a LOS that could potentially trigger GBS. In contrast to the strain used for CJCV1 (which was made from strain 3208), a natural variant of 3208 (named 3208.1) was selected that presents the two *O*-methyl phosphoramidate (MeOPN) transferases in the "on" status to ensure that there is an optimum amount of MeOPN on the capsule. The CPS is conjugated to CRM₁₉₇, a non-toxic mutant protein of diphtheria toxin at a CPS: CRM₁₉₇ ratio of 2:1. The CJCV2 vaccine product was manufactured at Inventprise LLC (Redmond, Washington) with final fill and finish completed by The University of Iowa Pharmaceuticals (Iowa City, Iowa), both performed under current Good Manufacturing Practices (cGMP) conditions.

- **Role of this study in clinical development**

This will be a Phase 1, first-in-human study of CJCV2 (1, 3, or 10 µg), with or without a fixed dose of ALFQ (200 µg 3D-PHAD® and 100 µg QS-21) to evaluate the safety and immunogenicity of the vaccine. A successful study will provide data for an increased number of subjects to receive an optimal CJCV2 dose (with or without adjuvant), and to potentially evaluate vaccine efficacy in a controlled human infection model (CHIM) with *C. jejuni* strain CG8421.

- **Prior studies of the study product**

Under US Army sponsorship, the Naval Medical Research Center (NMRC) recently completed a Phase 1, first-in-human trial with the prototype *C. jejuni* CPS vaccine conjugated to CRM₁₉₇, called CJCV1 (ClinicalTrials.gov Identifier: NCT02067676). The vaccine was manufactured using NIAID funding (NIH U01 AI082105) and delivered intramuscularly with AH. Forty-eight subjects (eight per group) received two doses of 2, 5, or 10 µg of the CJCV1 intramuscularly with or without 125 µg of AH on Days 0 and 28. There were no vaccine-related SAEs or unanticipated events. The vaccine was well-tolerated, with all vaccine-related AEs being mild to moderate vaccine site pain or tenderness. Irrespective of the CJCV1 dose delivered, only 6 of 48 subjects (12.5%) seroconverted against the CPS.

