## 6.5. Missing Data

All attempts will be made to collect all data per protocol. As missing data are expected to be minimal, no imputation will be performed for missing values. Any data point that appears to be erroneous or inexplicable based on clinical judgment will be investigated as a possible outlier. If data points are identified as outliers, sensitivity analyses will be performed to examine the impact of including or excluding the outliers. Any substantive differences in these analyses will be reported.

All immunogenicity variables have a lower limit of quantification (LLOQ). Results that are <LLOQ will be imputed as the limit of detection (LOD) in calculations of summary statistics in tabular and graphical displays. The CRM197-specific IgG and IgM assays have a 3-fold titration series, so the imputed value will be  $LOD = 1/3 * LLOQ$ . The *C. jejuni* capsule-specific serum IgG and IgM and ALS IgG assays have a 2-fold titration series, so the imputed value will be  $LOD = 1/2 * LLOQ$ . Imputed values will be rounded to the nearest whole number for consistency with conversion of results from  $\log_{10}$  titer to titer. The number of results <LLOQ will be reported in tabular summaries.

Immune Response	LLOQ		
	Log 10 Titer	Titer	Imputed Titer when <LLOQ
C. Jejuni Capsule-specific IgG Serum Antibody	2.30	200	100
C. Jejuni Capsule-specific IgM Serum Antibody	2.30	200	100
CRM 197 -specific IgG Serum Antibody	3.00	1000	333
CRM 197 -specific IgM Serum Antibody	2.00	100	33
C. Jejuni Capsule-specific IgG ALS Antibody	0.70	5	3

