[Implementation note: The figure below is an example only. The figure will be paneled by cohort. Time points presented will be Study Days 1, 8, 29, 36, 57, 64, 85, and 113; results will be grouped by analysis time point. Include footnote, “Note: Error bars represent 95% confidence interval based on Student’s t distribution.”. The figure should use the Adjuvant Status Group attributes.]

Note: Error bars represent 95% confidence interval based on Student's t distribution.

Figures with similar format:

**Figure 13:** **Geometric Mean Time Trends of *C. jejuni* Capsule-Specific IgG Serum Antibodies by Treatment Group, PP Immunogenicity Population**

**Figure 14:** **Geometric Mean Time Trends of CRM197-specific IgG Serum Antibodies by Treatment Group, Full Immunogenicity Population**

**Figure 15:** **Geometric Mean Time Trends of CRM197-specific IgG Serum Antibodies by Treatment Group, PP Immunogenicity Population**

**Figure 16:** **Geometric Mean Time Trends of *C. jejuni* Capsule-specific IgG ALS by Treatment Group, Full Immunogenicity Population**

*[Implementation Note: Time points presented will be Study Days 1, 8, 36, and 64.]*

**Figure 17:** **Geometric Mean Time Trends of *C. jejuni* Capsule-specific IgG ALS by Treatment Group, PP Immunogenicity Population**

*[Implementation Note: Time points presented will be Study Days 1, 8, 36, and 64.]*

**Figure 18:** **Geometric Mean Time Trends of *C. jejuni* Capsule-specific IgM Serum Antibodies by Treatment Group, Full Immunogenicity Population**

[figure not shown]
**Figure 19:** **Geometric Mean Time Trends of *C. jejuni* Capsule-specific IgM Serum Antibodies by Treatment Group, PP Immunogenicity Population**

**Figure 20:** **Geometric Mean Time Trends of CRM197-specific IgM Serum Antibodies by Treatment Group, Full Immunogenicity Population**

**Figure 21:** **Geometric Mean Time Trends of CRM197-specific IgM Serum Antibodies by Treatment Group, PP Immunogenicity Population**

**Figure 22: Scatterplot and Spearman's Correlation of Cumulative Estimated CJCV2 Dose and *C. jejuni* Capsule-specific IgG Serum Antibodies by ALFQ Status and Vaccination, Full Immunogenicity Population**

*[Implementation Note: The calculations for the correlations in these figures should match the calculations in the corresponding tables. The below is an example figure. The figure should use the Cohort Group attributes.]*

Figures with similar format:

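### When every result in a cell is below LLOQ, the SAP's t interval has zero width, and with about 80% or more below LLOQ the GMT interval is centred on the imputed constant

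*SAP*

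**What the plan says.** SAP 6.1 sets one interval method for all geometric means: "Confidence intervals for Geometric Mean Titer (GMT) and Geometric Mean Fold-Rise (GMFR) will be calculated using a" Student's t distribution. SAP 6.5 sets one rule for low results: "Results that are <LLOQ will be imputed as the limit of detection (LOD) in calculations of summary statistics in tabular and graphical displays".

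The constant depends on the assay:
- The *C. jejuni* "capsule-specific serum IgG and IgM and ALS IgG assays have a 2-fold titration series", so half the LLOQ is used: 200 becomes 100 for serum IgG and IgM, and 5 becomes 3 for ALS.
- The CRM197 "assays have a 3-fold titration series, so the imputed value will be" one third of the LLOQ: 1000 becomes 333 for IgG, and 100 becomes 33 for IgM.

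SAP 3.3 defines fold-rise as the post-vaccination value divided by the baseline value. The Table 15 footnotes repeat both the t method and the imputation. The Figure 12 note says "Error bars represent 95% confidence interval based on" the t distribution, and Figures 13-21 share that format.

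Neither document has a rule for a cell without variation, a censored-data method, or a sensitivity analysis of the imputation. The sensitivity analysis in SAP 6.5 concerns outliers only.

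**The concern.** A t interval measures uncertainty from the spread of the values. Once results below LLOQ are all set to one number, that spread is partly or wholly an artefact of the substitution. In the extreme case the plan reports perfect precision for a cell in which nothing was quantified. The SAP treats a comparable lack of information very differently for adverse events, where no event in 10 participants is reported as 0-31%.

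These t intervals are the only ones planned for GMT and GMFR, which are reported for the secondary capsule IgG results and for all exploratory assays. A reader comparing groups or visits, above all in the figures, could take a missing error bar for a precise estimate.

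**Working it through.** **Inputs.** n = 10 per group (SAP 5); LLOQ 200 and imputed value 100 for capsule IgG (SAP 6.5); t interval (SAP 6.1). The documents give neither the SD of log10 titer nor the share below LLOQ. I assume normal log10 titers with SD 0.3, 0.5 or 0.7, and vary the share.

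**The plan's own figures.** The SAP says "using an exact binomial interval for no observed adverse events within the 10 participants per group yields a 95% confidence interval (CI) of 0-31"%. The Clopper-Pearson upper limit is 1 − 0.025^(1/10) = 0.3085, so this reproduces. The imputed titers also reproduce: 200/2 = 100, 1000/3 = 333, 100/3 = 33, and 5/2 = 2.5, rounded to 3.

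**All ten below LLOQ (exact, no assumption).** Every log10 value is 2, so s = 0. The interval 10^(mean ± 2.262 × s/√10) is 100.0 (100.0, 100.0). If baselines are also all below LLOQ, every fold-rise is 100/100 = 1 and the GMFR is 1.00 (1.00, 1.00).

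**How often.** At one visit, P(all ten below LLOQ) = p^10: 0.8^10 = 0.107, 0.9^10 = 0.349, 0.95^10 = 0.599.

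**Nearly all below LLOQ.** Nine at 100 and one at 200: mean log10 = 2.0301, s = 0.0952, half-width 2.262 × 0.0952/√10 = 0.0681, giving 107.2 (91.6, 125.4). Eight at 100 plus 200 and 400 gives 123.1 (88.1, 172.1).

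**GMT coverage.** 100,000 simulated groups of 10 per setting; nominal level 95%.

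| Share <LLOQ | SD 0.3 | SD 0.5 | SD 0.7 | Zero-width |
|---|---|---|---|---|
| 50% | 92% | 95% | 94% | 0.1% |
| 60% | 91% | 94% | 88% | 0.6% |
| 70% | 91% | 85% | 33% | 3% |
| 80% | 88% | 3% | 0% | 11% |
| 90% | 3% | 0% | 0% | 35% |
| 95% | 0% | 0% | 0% | 60% |

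**Bias or width?** At 80% and SD 0.5 the true GMT is 75.9, below the constant 100, and the interval lies wholly above it in 97% of runs. At 80% and SD 0.3 the true GMT is 111.8, above the constant, and coverage is 88%. The collapse therefore depends mainly on which side of the constant the truth lies. Width also shrinks: at 80% and SD 0.5 the median upper/lower ratio is 2.14, against 4.9 without censoring.

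**GMFR coverage.** Assumed: baseline log10 SD 0.3, and post = baseline + rise + noise with SD 0.2.

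| Baselines <LLOQ | No rise | 2-fold | 4-fold |
|---|---|---|---|
| 99% | 100% | 11% | 8% |
| 95% | 100% | 46% | 50% |
| 84% | 99% | 83% | 90% |
| 63% | 96% | 95% | 95% |

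The failure needs both censored baselines and a real rise. In most of those settings the interval is wider than the uncensored one, so the fault there is bias.

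**The case against.** Much of the case on the other side stands.

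- **The tables already warn.** Table 15 prints n, a count of results below LLOQ, and the minimum and maximum beside each GMT, with a footnote on imputation. Listing 8 marks imputed values. A careful reader would see ten of ten below LLOQ next to the collapsed interval. The interval is still printed, though, and the Figure 12 note carries no such flag.
- **Responder results are unaffected by collapse.** The 4-fold-rise endpoint uses exact intervals.
- **Peak values are less exposed.** A zero-width peak-titer row needs all ten participants below LLOQ at every post-vaccination visit, so the single-visit chances of 11%, 35% and 60% do not apply to it.
- **Few but strong responders.** Eight results below LLOQ plus 3200 and 6400 give 214 (67.5, 680.9), which is not narrow in absolute terms.

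A reader might infer that the unadjuvanted arms will be mostly below LLOQ because, with the predecessor vaccine, "only 6 of 48 subjects (12.5%) seroconverted against the CPS". The documents do not support that. Seroconversion is not the share below LLOQ, since a participant with a quantifiable baseline and no rise also fails to seroconvert. The figure pools groups with and without aluminum hydroxide, and it comes from an earlier product with a different dose schedule and adjuvant.

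**Conclusion.** The zero-width interval is exact, follows from two stated rules, and nothing else in the plan prevents it. How often it will occur is unknown, because the documents give no titer distribution.

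The wider problem is conditional. At about 80% or more below LLOQ, or from about 70% if the log10 SD is 0.5 or more, the GMT interval can miss the truth badly, mainly because it is centred on the imputed constant. GMFR is similarly biased when most baselines are below LLOQ and titers really rise. These statements rest on normal log10 titers, the assumed SDs and, for GMFR, the assumed within-person variation.

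A reader might go further and conclude that every cell with more than half its results below LLOQ has an unusable interval. The calculation does not support this: at 50-60% coverage is 91-95% for SD 0.3-0.5. Nor should the low coverages be read as a pure width failure.

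The outputs are secondary and exploratory, descriptive and untested. A modest correction is warranted.

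**What to change.** Add to SAP 6.1, the Table 15 note and the Figure 12 note, and carry it to the tables and figures that share their format:

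1. If all results in a cell are below LLOQ, show the GMT as <LLOQ, with no CI and no error bar.
2. Show GMFR as not estimable when all baseline and post-vaccination results are below LLOQ.
3. In such cells give the exact Clopper-Pearson CI for the proportion at or above LLOQ (0/10: 0-31%).
4. Footnote or flag GMT cells and figure points with a large share below LLOQ (for example 80% or more), and GMFR cells with a large share of baselines below LLOQ, as driven by the imputed constant. The GMFR flag must look at baselines, because the post-vaccination cell may itself be well quantified.
5. Keep the planned t interval elsewhere.

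A left-censored normal likelihood can be an optional sensitivity analysis where enough results are quantified. With five of ten quantified (220, 260, 300, 400, 500) it gives 204.4 (100.9, 298.9), against 179.3 (112.3, 286.2) as planned. With only two (220 and 400) it gives 112.7 (3.3, 200.2), against 124.3 (88.2, 175.2), and says little.

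The cost is a few lines of SAP text and a small programming rule. No new data are needed. The downside is that some cells show no interval.
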